Systemic reactions have been reported in individuals who received the rVSVΔG-ZEBOV-GP vaccine (17, 26). These events generally occur within the first 12 to 24 hours post-vaccination, are mild to moderate in severity, and resolve within 1 or 2 days. They include headache, fever, feeling "feverish", chills, arthralgia, myalgia, and less commonly, gastrointestinal symptoms. These early symptoms are associated with activation and release of cytokines and chemokines (27). For these and other systemic symptoms commonly seen in investigational vaccine studies, monitoring will be performed throughout the study and symptoms will be addressed as required to maximize subject safety. On occasion, individuals may feel lightheaded or faint after the act of injection (often an emotionally-related vasovagal reaction).

Late Systemic Reaction

Transient post-vaccination AEs seen with rVSVAG-ZEBOV-GP primarily include arthritis, and macular, papular, or vesicular rash (17). In a Phase 1b study of 513 healthy volunteers (26), self-limited, post-vaccination arthritis occurred in 4.5% (19 of 418) of vaccinees (median onset 12.0 days [interquartile range (IQR) 10–14]; median duration 8.0 days [IQR 6–15]) versus 3.2% (three of 94) of controls (median onset 15.0 days [IQR 6–20]; median duration 47.0 days [IQR 37–339]), with no apparent dose relationship. Post-vaccination dermatitis occurred in 5.7% (24 of 418) of vaccinees (median onset 9.0 days [IQR 2–12]; median duration 7.0 days [IQR 4–9]) versus 3.2% (three of 94) of controls (median onset 5.0 days [IQR 3–53]; median duration 33.0 days [IQR 5–370]). These could also be observed with PHV01.

Other Potential Risks

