4.4.2. Adverse Events

AEs will be assessed by evaluating reactogenicity (local reactions and systemic reactions) and the occurrence of post-vaccination solicited local reactions and systemic AEs through day 15. Solicited AEs for days 16-29 are limited to instances of neurological signs and symptoms, arthritis, and rash. Arthritis, rash, and neurologic events should be evaluated throughout the study and may include expert consultation.

All AEs (including solicited AEs) will be coded using the MedDRA coding system and displayed in tables and data listings using system organ class (SOC) and preferred term (PT). Note that solicited and unsolicited AEs will be analyzed and presented separately. The severity of all AEs will be graded in accordance with the FDA document "Guidance for Industry: Toxicity Grading Scale for Healthy Adult and Adolescent Volunteers Enrolled in Preventive Vaccine Clinical Trials" described in Section 5.

Analyses of AEs will be performed for those events that are considered treatment-emergent, where treatment-emergent is defined per protocol as any AE with onset after the administration of study medication.

All AEs occurring on-study will be listed in subject data listings.

By-subject listings also will be provided for the following: subject deaths, SAEs, AEs leading to withdrawal, solicited local site AEs, solicited systemic AEs, MAAEs, and AESIs.

Solicited AEs are predefined local events at the injection site and systemic events for which the subject is specifically questioned and facilitated by use of memory aides.

The following local AEs will be solicited:

- Arm Pain [CRF term: Pain at Site of Injection]
- Local Tenderness [CRF term: Tenderness at Site of Injection]
- Erythema (Redness) [CRF term: Redness at Site of Injection]
- Induration (Swelling/Firmness) [CRF term: Swelling at Site of Injection]

Note: CRF term in the square brackets refers to the term used on the Adverse Event Case Report Form to capture the local solicited AEs.

The following systemic (non-injection site) AEs will be solicited:

- Subjective Fever [CRF term: Subjective Fever]
- Objective Fever [CRF term: Fever]
- Chills [CRF term: Chills]
- Sweats [CRF term: Sweats]
- Myalgia [CRF term: Myalgia]
- Arthralgia [CRF term: Arthralgia]
- Joint Swelling [CRF term: Joint Swelling]
- Joint Tenderness [CRF term: Joint Tenderness]
- Fatigue [CRF term: Fatigue]

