- Gastrointestinal Symptoms (symptoms include nausea, vomiting, abdominal pain, and diarrhea) [CRF terms: Nausea, Vomiting, Abdominal Pain, Diarrhea]
- Mucosal Lesions [CRF terms: Mucosal Lesion, Mouth Ulcer]
- Skin Lesions [CRF terms: Skin Lesion]
- Neurological Symptoms (symptoms include blurry vision, changes in balance or coordination, confusion, disorientation, dizziness, severe headache, shaking or body tremors, slurred speech, tingling or numbness, weakness or feeling weak) [CRF terms: Blurry Vision, Changes in Balance or Coordination, Confusion, Disorientation, Dizziness, Severe Headache, Shaking or Body Tremors, Slurred Speech, Tingling or Numbness, Weakness or Feeling Weak]

Neurological symptoms described above will be considered as solicited neurological AEs. Specific joint related (arthralgia, joint swelling, and joint tenderness) will be considered as solicited rheumatologic AEs; and mouth ulcer or skin/mucosal lesions will be considered as dermatologic AEs.

All TEAEs that cause a subject to seek medical care (including extra visits to the clinical site) are considered to be MAAEs.

Additionally, certain neurologic/hematologic/immunologic diseases are considered as AESIs in the study. Such AESIs include pneumonitis, acute respiratory distress syndrome, multiorgan failure, a hemorrhagic diathesis, certain neurologic events (encephalitis, myelitis, aseptic meningitis, optic neuritis, transverse myelitis, generalized convulsions, Guillain-Barré Syndrome, acute disseminated encephalomyelitis), thrombocytopenia ≥ Grade 2, anaphylaxis, and vasculitides.

Summary tables will be generated for the following:

- Solicited local site AEs within 7 days, and 8 to 14 days following vaccination by Solicited Term and severity
- Solicited systemic AEs within 7 days, and 8 to 14 days following vaccination by Solicited Term and severity
- Solicited neurological AEs within 7 days, 8 to 14 days, 15 to 28 days and up to day 181 following vaccination by Solicited Term and severity
- Unsolicited AEs within 7 days, 8 to 14 days, 15 to 28 days and up to day 181 following vaccination by SOC, PT, relatedness, and severity

- Solicited Rheumatologic AEs within 28 days and up to day 181 following vaccination by Solicited Term and severity
- Solicited Dermatologic AEs within 28 days and up to day 181 following vaccination by Solicited Term and severity
- SAEs up to day 181 by SOC, PT and relatedness
- MAAEs up to day 181 by SOC, PT and relatedness

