- AESIs at baseline, and up to day 181 by SOC, PT and relatedness

The number and percentage of subjects with any AE type as described above will be summarized by treatment group and combined PHV01 group. Adverse events are summarized by subject incidence rates; therefore, in these tabulations, each subject will contribute once (i.e., the most related occurrence or the most intense occurrence) to each of the incidence rates in the analysis regardless of the number of episodes. Tabulation by relatedness to study vaccine will be categorized as Related (Definite, Probable, Possible) or Not related; while tabulation by severity will be graded as Grade 1 (Mild), Grade 2 (Moderate), Grade 3 (Severe), Grade 4 (Potentially life-threatening).

Additionally, a symptom score will also be used to summarize solicited local and systemic AEs. The symptom score is a scalar quantity that summarizes the overall severity of a subject's solicited AE experience. The symptom index for a given AE will be defined as individual unique toxicity grades reported for each TEAE multiplied by the duration of the TEAE. The individual symptom indices will then be summed for each subject to obtain their symptom score. Larger scores are indicative, overall, of more severe and/or AEs of longer duration; smaller scores are indicative, overall, of less severe and/or AEs of shorter duration.

If an AE is ongoing at the end of the observation period, the length of the observation period post vaccination will be used in the calculation of symptom index. If the severity is missing for any particular AE, then the corresponding symptom index will also be set to missing.

Symptom scores will be summarized descriptively by treatment group and the combined PHV01 treatment group. Symptom scores will be calculated separately for all solicited local and systemic AEs which started within 14 Days of vaccination. The mean, standard deviation, median, minimum, and maximum values will be tabulated.

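### The dedicated joint and skin AE tables count each subject once over 28 days, and no planned table isolates onset 15 to 28 days after vaccination

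*SAP*

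**What the plan says.** All the tabulation rules are in SAP 4.4.2 (Adverse Events).

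- Joint events: "Solicited Rheumatologic AEs within 28 days and up to day 181 following vaccination by Solicited Term and severity".
- Skin and mucosal events: "Solicited Dermatologic AEs within 28 days and up to day 181 following vaccination by Solicited Term and severity".
- By contrast: "Unsolicited AEs within 7 days, 8 to 14 days, 15 to 28 days and up to day 181 following vaccination". Solicited neurological AEs have the same four windows.
- Counting rule: "each subject will contribute once (i.e., the most related occurrence or the most intense occurrence"), applied to each incidence rate however many episodes the subject had.
- Arthralgia, joint swelling, joint tenderness, mucosal lesions and skin lesions also appear under the line "The following systemic (non-injection site) AEs will be solicited". That category is summarised as "Solicited systemic AEs within 7 days, and 8 to 14 days following vaccination by Solicited Term and severity".
- The same section then relabels the joint terms as rheumatologic and the skin and mucosal terms as dermatologic. It does not say whether they remain in the systemic table.
- On Days 16-29 solicitation continues for three categories only: neurological symptoms, arthritis and rash.

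SAP 1.2.5.1 makes arthritis and skin/mucosal lesions up to Day 29 a primary safety endpoint.

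**The concern.** Protocol 1.5.1 describes two different reactions to the related Ebola vaccine. Arthralgia is part of an early systemic reaction that begins within 12 to 24 hours and is gone in a day or two. Arthritis is a late reaction: "self-limited, post-vaccination arthritis occurred in 4.5% (19 of 418) of vaccinees", with median onset 12 days and interquartile range 10 to 14.

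The protocol itself separates joint events by onset day when it triggers the arthritis work-up. The dedicated SAP tables do not. A subject with arthralgia on Day 2 and again on Day 20 appears once in the arthralgia row, at the worse of the two grades and with no sign that there were two episodes.

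Three categories are still being solicited on Days 16-29, yet only the neurological one has a table for that period, and no reason is given for the difference. What is at stake is whether the summary tables can show late joint and skin events by dose. These tables feed the interim analysis that guides dose selection (SAP 3.12), and results summarised by treatment group may be shown to outside decision-makers (Protocol 7.2).

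**Working it through.** **1. The plan's own precision figures.** SAP 3.1 gives exact 95% upper bounds for zero events: 1 - 0.025^(1/10) = 30.85% for a dose group and 1 - 0.025^(1/30) = 11.57% for all vaccinees. These match the stated 30.9% and 11.6%. They are not in dispute, but they show the resolution available.

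**2. Windows side by side** (days after vaccination, SAP 4.4.2)

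| Category | 0-7 | 8-14 | 15-28 | Cumulative tables |
|---|---|---|---|---|
| Neurological (solicited) | yes | yes | yes | to day 181 |
| Unsolicited | yes | yes | yes | to day 181 |
| Systemic (solicited) | yes | yes | no | none |
| Rheumatologic, dermatologic | no | no | no | to 28 days, to day 181 |

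If the joint and skin terms stay in the systemic table, they gain the first two windows. If they were moved out, they have none. Neurological symptoms are in the same systemic list and yet have their own 0-7 and 8-14 day table, so removal is a plausible reading. The 15-28 column is empty on both readings.

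**3. Why subtraction fails.** For one term, let A, B and C be the sets of subjects with an onset in 0-7, 8-14 and 15-28 days. On the favourable reading the tables give |A|, |B| and |A or B or C|. Take |A| = 7, |B| = 2 and a 28-day total of 9, with A and B disjoint. Then |C| can be anything from 0 to 9, because a subject already in A or B adds nothing to the total when a later episode occurs.

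**4. What the cumulative row can conceal.** Ten subjects with early episodes only, or seven with early and three others with late episodes, both display as 10/30 = 33% (95% CI 17.3% to 52.8%). A late-onset row would show 0/30 (0 to 11.6%) or 3/30 (2.1% to 26.5%).

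**5. Expected numbers.**
- Late arthritis rate l: 19/418 = 4.5% (Protocol 1.5.1).
- Expected cases: 30 x 0.045 = 1.35 in all vaccinees (chance of at least one, 75%) and 0.45 in a dose group (37%).
- An upper quartile of 14 days puts at most about a quarter of onsets after day 14: 1.35 x 0.25 = 0.34 cases. About half or more fall in 8-14 days.

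**6. Absorbed cases.** The documents give no early arthralgia rate e for PHV01 or the related vaccine, so a range is assumed. Early and late events are taken as independent, and every late case is taken to be recorded as arthralgia.

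Cumulative rate = 1 - (1 - e)(1 - l). Expected absorbed = 30 x l x e. Chance of at least one absorbed = 1 - (1 - l x e)^30.

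| Assumed e | Cumulative rate | Added by late events (points) | Expected absorbed | Chance of at least one | Absorbed with onset after day 14 (at most) |
|---|---|---|---|---|---|
| 10% | 14.05% | 4.05 | 0.135 | 12.7% | 0.03 |
| 20% | 23.6% | 3.60 | 0.27 | 23.8% | 0.07 |
| 30% | 33.15% | 3.15 | 0.405 | 33.5% | 0.10 |

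Protocol 3.1.4 reports arthritis incidence from 0% to 23.5% across studies. At 23.5% the chance of at least one absorbed case is 51%, 76% and 89% for the same three values of e.

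**The case against.** The strongest objection is to a reading that is easy to infer: that joint and skin events are tabulated only cumulatively, so that the plan hides the delayed arthritis signal. The documents do not support that.

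- As written, the terms are in the systemic list, and the systemic table separates 0-7 from 8-14 days. Most of the cited late onsets fall in the second window.
- Tables are by solicited term. Joint swelling and joint tenderness have their own rows, and Protocol 1.5.1 names arthralgia, not swelling, among the early reactions.
- The early/late contrast is documented for joints. No early rash is listed as part of the acute reaction. The cited dermatitis onset range (interquartile 2 to 12 days) merely spans both periods.
- The primary endpoint is cumulative to Day 29, so the 28-day table matches it.
- Listings carry the relative study day (SAP 3.2), and joint and skin examination findings are listed (SAP 4.4.6). With 36 subjects, timing can be read off by hand.
- Protocol 3.1.4 puts arthritis onset typically within a week, so a 0-7 day window will not cleanly separate the two reactions either.
- With 0.45 late cases expected per dose group, no layout will give a precise rate by dose.

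All of this limits the point, but three things remain. The SAP leaves it open whether the systemic table keeps these terms. Days 15-28 have no window on any reading. Listings show individual days but give no summary by treatment group.

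**Conclusion.** The point holds in a limited form. The dedicated rheumatologic and dermatologic tables have no onset windows, and a subject's early and late episodes of the same term collapse into one count. No planned table isolates joint or skin onset 15 to 28 days after vaccination, although arthritis and rash are still solicited then.

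The likely numerical effect is small. At the 4.5% rate, between 0.135 and 0.405 absorbed cases are expected among 30 vaccinees, and at most 0.03 to 0.10 of these would have onset after day 14. Those figures rest on an assumed early arthralgia rate of 10% to 30%, on independence, and on the related vaccine's rate and onset distribution carrying over to PHV01. They rise if arthritis is nearer the upper end of the reported range.

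This is a gap in presentation, not in data collection, and it does not make the late signal unrecoverable. It deserves correction because only one or two late cases are expected, so misplacing one changes the picture, and because the SAP already uses the needed windows elsewhere.

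**What to change.** In SAP 4.4.2:

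1. Tabulate solicited rheumatologic and dermatologic AEs by onset window: 0-7, 8-14 and 15-28 days, and after day 28 to day 181. A subject contributes once per term per window.
2. Keep the cumulative 28-day table, which matches the primary endpoint.
3. State whether the joint and skin terms also remain in the solicited systemic table.
4. Summarise onset day and duration by treatment group for all joint and skin events, not only those after day 7, since Protocol 3.1.4 places arthritis onset typically within the first week.
5. Flag events whose onset date was imputed. SAP 3.10 moves a partial date in the month of vaccination to the vaccination day, and so into the first window.

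Separately, the protocol's threshold for late joint events is day 5 in sections 3.1.4, 5.5.3 and 6.3 but day 6 in section 6.2. These passages must be reconciled before either is used as an analysis cut. The windows above do not depend on the answer.

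The cost is a few extra table shells, many of them sparse. No new data are needed: the SAP already relies on onset dates and durations, and under Protocol 6.5 the eCRF records the highest grade over continuous days, so separate episodes stay distinguishable.

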6.2. ASSESSMENT OF SUBJECTS WITH JOINT-RELATED ADVERSE EVENTS

In the event of cases of acute aseptic arthritis, data collection, analysis, and presentation should be performed in accordance with Brighton collaboration guidelines (45) and may require expert consultation.

Subjects who have joint pain on or after day 6 following administration of vaccine will undergo assessment by the PI within 72 hours of onset with a targeted exam, guided by the Arthritis Pathway titled "Evaluation of Subjects with Joint Signs and Symptoms" (Figure 2). In brief:

• The subject self-monitors for joint pain or rash. The subject should identify the primary source of pain and any other affected joints.

- Determine if findings of arthritis are present, defined as any 1 of the following:
 - o Clinically significant reduction in range of motion
 - o Synovitis (tenderness or swelling or redness or heat)
 - o Effusion
- Document findings using the standardized form.
- If arthritis present, draw a CBC, serum chemistries (including BUN, creatinine, and uric acid), PT/PTT, fibrinogen, a rheumatology panel (CRP, RF, anti-CCP, C3, C4, ANA, anti-CCP, sample for cytokine levels), and obtain a urinalysis.

If arthritis is present, the subject should be assessed either by a Physician Investigator who is proficient in arthrocentesis or a consultant. If effusion is confirmed, consent should be obtained for the subject to undergo arthrocentesis for joint fluid assessment.

[figure not shown]
- The synovial fluid assessment should include:
 - Cell count with differential
 - o Crystal examination
 - o Culture for bacteria, and virus isolation
 - o RT-qPCR for vaccine viral RNA

Follow-up is determined by clinical course. If symptoms are mild (Grade 1), follow up as per Schedule of Events: days 8, 15, and 29, then monthly until resolved. If at day 29 the ongoing symptoms are Grade 2 or worse, follow weekly until mild (Grade 1) and then schedule as above. Repeat BUN, creatinine, uric acid, and rheumatology panel, and obtain urinalysis at follow up visits until resolved. The Investigator may evaluate the subject more frequently if clinically indicated.

If rash is present on any visit, this triggers the Dermatology Pathway, as outlined in Section 6.3.

Figure 2: Evaluation of Subjects with Joint Signs and Symptoms

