7.5.1. Analysis Addressing the Primary Study Objective (Safety)

Solicited symptoms occurring during the 28 days following vaccination will be summarized by treatment group and by relatedness. The incidence and severity of solicited AEs to the vaccine over the 28-day follow-up period will be calculated. Presentations will include the number and percentage of subjects with at least 1 local AE, and at least 1 general (systemic) AE, as well as the incidence of each AE individually.

The number of subjects with at least 1 incidence of an unsolicited AE reported up to 28 days after vaccination will also be summarized overall and by treatment group. The severity and temporal relationship of the unsolicited AEs to vaccination will also be assessed. Presentations will also summarize unsolicited AEs by grade and vaccine-relatedness. Serious AEs occurring at any point during the trial will be summarized and relatedness to vaccine will be assessed. The incidence rate of solicited AEs may be compared between each treatment group and placebo using Fisher's exact test and logistic regression.

The level of vaccinemia (on days 1 [at 0 and 6 hours], 2, 4, 8, 15, and 29) and shedding will be assessed on all subjects. The proportion of subjects with detected vaccinemia, as well as the geometric mean and AUC of vaccinemia level, will be presented at each time point where data are collected. The relationship between vaccinemia level and dose will be explored in a mixed model for repeated measures (MMRM) analysis that incorporates dose level, time, and other potential predictive factors. A similar model will be used to explore the relationship between dose and the AUC of the vaccinemia level.

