1.2.5. Safety and Immunogenicity Parameters

1.2.5.1. Safety Parameters

Safety will be assessed by analysis of the occurrence of treatment emergent adverse event (TEAE) and vaccine viremia, as well as by adverse changes in laboratory evaluations (chemistry, hematology, urinalysis, etc.), vital signs, and physical findings, including neurologic examinations. Solicited AEs will be collected systematically through Day 29; unsolicited TEAEs, medically attended adverse events (MAAEs), SAEs, and AESIs will be collected for the entire duration of a subject's participation in the study with the help of Memory Aids reviewed at every visit The primary safety endpoints are:

- Incidence and severity of solicited injection site AEs (arm pain, local tenderness, erythema (redness), induration (swelling/firmness) and systemic AEs (objective fever, subjective fever, chills, sweats, headache, myalgia, arthralgia, fatigue, nausea, vomiting) and neurological AEs (blurry vision, changes in balance or coordination, confusion, disorientation, dizziness, severe headache, shaking or body tremors, slurred speech, tingling or numbness, weakness or feeling weak) between Days 1 and 8, Days 9-15, and up to Day 29 after vaccination, per treatment group (active vaccination versus placebo).
- Incidence and severity of unsolicited AEs between Days 1-8, Days 9-15, and up to Day 29 after vaccination, per treatment group (active vaccination versus placebo) and stratified by relatedness, i.e., not related vs related.
- Incidence and severity of arthritis and skin/mucosal lesions up to Day 29 after vaccination using standard case definitions and stratified by relatedness. This includes where possible quantitative reverse transcription polymerase chain reaction (RT-qPCR) for detection of PHV01 and lesion biopsy for histopathology.
- Incidence of SAEs observed up to Day 181 and stratified by relatedness.
- Incidence and severity of MAAEs observed up to Day 181 and stratified by relatedness.
- Physical and neurological examination results, vital signs, normal and abnormal clinical laboratory values (hematology and clinical chemistry, urinalysis).

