4.4.6. Vital Signs and Physical Examination

The actual value and change from baseline (Day 1) to each on-study evaluation will be summarized for vital signs.

Vital sign measurements will be presented for each subject in a data listing.

All physical examination, dermatologic, joint assessment and neurologic exam findings will be presented in a data listing.

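### SAP 4.4.2 only partly delivers the primary arthritis and skin/mucosal endpoint: the tables have no relatedness split, and none counts arthritis by a case definition

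*SAP*

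**What the plan says.** The endpoint in SAP 1.2.5.1, which matches protocol 3.1.1, is "Incidence and severity of arthritis and skin/mucosal lesions up to Day 29 after vaccination using standard case definitions and stratified by relatedness". Protocol 7.5.1 adds, for solicited events in general: "Solicited symptoms occurring during the 28 days following vaccination will be summarized by treatment group and by relatedness".

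The SAP 4.4.2 table list answers with "Solicited Rheumatologic AEs within 28 days and up to day 181 following vaccination by Solicited Term and severity" and "Solicited Dermatologic AEs within 28 days and up to day 181 following vaccination by Solicited Term and severity". The content of the joint table is fixed by "Specific joint related (arthralgia, joint swelling, and joint tenderness) will be considered as solicited rheumatologic AEs". The dermatologic terms are mouth ulcer and skin or mucosal lesions.

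Examination results are handled in SAP 4.4.6: "All physical examination, dermatologic, joint assessment and neurologic exam findings will be presented in a data listing".

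On definitions, protocol 6.2 states: "In the event of cases of acute aseptic arthritis, data collection, analysis, and presentation should be performed in accordance with Brighton collaboration guidelines". It then lists three kinds of examination finding (restricted motion, synovitis, effusion), any one of which counts as arthritis, and asks for them on a standardized form. Protocol 6.3 points to a separate Brighton guideline for rash. The SAP names neither guideline and does not repeat the 6.2 list.

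**The concern.** The endpoint has two qualifiers, relatedness and a standard case definition. The SAP repeats both in its endpoint list, and neither appears in the tables meant to report it. A programmer following the table list would produce symptom rows by severity. The report would then have no related/unrelated incidence for joint or skin events, and no figure that could be called the incidence of arthritis.

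Arthritis is a recognised late reaction of this vector class, so readers will look for that figure. Protocol 3.1.4 reports incidence from 0% to 23.5% across studies of the related vaccine and puts the spread down partly to how arthritis was defined and diagnosed. If the rule is not written down, it will be chosen after cases are seen. Under protocol 3.3.2 most Sponsor and CRO staff are unblinded during the study.

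**Working it through.** **1. The plan's own AE figure.** The zero-event Clopper-Pearson upper bound is 1 − 0.025^(1/n). For n = 10 it is 0.3085 (the plan prints 30.9%), and for n = 30 it is 0.1157 (printed 11.6%). These reproduce to rounding, and this point disputes no number in the plan.

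**2. Endpoint elements against the two tables.**

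| Element | Rheumatologic table | Dermatologic table |
|---|---|---|
| Subject incidence | Yes, per symptom | Yes, per lesion term |
| Severity | Yes | Yes |
| To Day 29 (28 days, vaccination = Day 1) | Yes | Yes |
| Dose groups, combined PHV01, placebo | Yes | Yes |
| Relatedness | No | No |
| Case definition | No | Not stated |

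**3. Is the missing relatedness deliberate?** In the 4.4.2 list, the unsolicited, SAE, MAAE and AESI tables name relatedness and none of the solicited tables does. SAP 1.2.5.1 drops relatedness from the general solicited-AE bullet, which could be a choice. It keeps relatedness in the arthritis and skin/mucosal bullet, so for this endpoint the SAP disagrees with itself as well as with protocol 7.5.1. SAP section 6 records no such change. The 4.4.2 sentence on Related / Not related defines the categories but assigns them to no table.

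**4. Could another table supply the arthritis count?**
- *Unsolicited AEs.* This table has preferred term, relatedness and severity, but reports within 7 days, 8 to 14, 15 to 28, and to Day 181, with no cumulative Day 29 column. The rule to record a diagnosis in place of symptoms (protocol 6.6.1) covers unsolicited AEs. Both documents describe arthritis as solicited in days 16-29, so it is not clear that a diagnosed case would be placed here.
- *MAAEs.* The specification is "MAAEs up to day 181 by SOC, PT and relatedness". It has no severity, no Day 29 cut and no case status.
- *Joint listing.* It holds the findings but gives no incidence.

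**5. How often the rule would be needed.** The inputs are the rates in protocol 1.5.1 for the related Ebola vaccine: arthritis 19/418 and dermatitis 24/418 in vaccinees, and arthritis 3/94 in controls.
- Arthritis, 30 vaccinees: 30 × 19/418 = 1.36 expected; 1 − (399/418)^30 = 0.752.
- Arthritis, one dose group of 10: 10 × 19/418 = 0.45 expected; 1 − (399/418)^10 = 0.372.
- Dermatitis, 30 vaccinees: 30 × 24/418 = 1.72 expected; 1 − (394/418)^30 = 0.830.
- Arthritis, 6 placebo subjects: 6 × 3/94 = 0.19 expected; 1 − (91/94)^6 = 0.177.

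**The case against.** The strongest reply is that most of the endpoint is already reported. Incidence, severity, the 28-day window and the placebo comparison are all there, and the dermatologic terms match the lesions the endpoint names. That stands. A reader might infer that the endpoint is not delivered at all, and the tables do not support that. For skin/mucosal events the gap is the relatedness split and an unstated guideline.

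A reader might also infer that early arthralgia, which settles in a day or two, will be blended with later arthritis in one 28-day table. SAP 4.4.2 lists the joint terms among the solicited systemic AEs and tabulates those within 7 days and for days 8 to 14. Early symptoms are therefore separable, and blending is not a main harm.

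It is fair to say that a diagnosed arthritis may surface in the unsolicited or MAAE tables, and that one or two cases could be combined across windows by hand. That gives a count by preferred term, without a case definition. Joint swelling and tenderness do overlap the 6.2 synovitis criterion, and Memory Aid entries are confirmed with the subject. Restricted motion and effusion have no row, however, and the rows are not derived from the examination form.

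A further reply is that placebo handles background arthritis. It helps, but six subjects give only a 0.177 chance of one background case, so individual relatedness still adds information.

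It is tempting to claim that the choice of definition would reclassify subjects and shift the exact confidence bounds. The documents do not reproduce the Brighton criteria, so no difference between the definitions can be shown. Nor are exact intervals a planned output for AEs. The joint pathway's start day (day 6 in 6.2, day 5 in 3.1.4 and 6.3) is a wording matter, negligible against a quoted onset interquartile range of 10 to 14 days.

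**Conclusion.** The point holds in a limited form. Two tables lack a split that the endpoint and protocol 7.5.1 both require, and arthritis, a named primary safety outcome, has no count under a stated definition. Trial conduct is not in question. Relatedness is assigned to every AE by site physicians blinded to treatment, and joint findings are recorded on a standardized form, so what is missing is a reporting rule. It should be corrected because the endpoint is primary and roughly one arthritis case is likely.

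The expected counts assume that PHV01 behaves like the related Ebola vaccine and that subjects are independent. The relatedness gap is certain from the text. The case-definition gap is certain for the SAP. The joint form and the pathway figures are not available here and may carry a definition, but the SAP would still need to refer to it.

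**What to change.** 1. Add Related / Not related, as already defined in SAP 4.4.2, to the rheumatologic and dermatologic tables.
2. Add one table of arthritis cases to Day 29 by dose group, combined PHV01 and placebo, with severity and relatedness. Derive case status from the standardized joint form under one definition written into SAP 4.4.2. This can be the protocol 6.2 examination findings, or the Brighton definition cited there if the form holds every item it needs.
3. State in SAP 4.4.2 that skin/mucosal cases follow the guideline cited in protocol 6.3.
4. Settle this before results are unblinded. The documents do not show whether the Day 29 interim freeze has happened. If it has, fix the rule before final lock and document the date.

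The cost is one derivation, one extra table, a split in two tables and a check of the form. No new data or visits are needed.
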